4. Safety Review and Monitoring

- a) Independent Safety Monitor. The study will be monitored by the principal investigator, MD co-investigator and an Independent Safety Monitor. The Safety Monitor will be [name] MD, Associate Professor of Neurology and Molecular & Medical Genetics at OHSU. [name] will be notified immediately if a significant adverse event occurs, and then she, as Safety Monitor, together with the PI, will notify the OHSU IRB, the NIH, and the CRC. The role of the Safety Monitor will be:
 - i) The Safety Monitor will review the annual report and all adverse events prior to submission of the IRB review
 - ii) She will prepare a memo of her findings and recommendations to be included in the submission to the IRB with the annual report.
 - iii) If any serious unexpected adverse event occurs, the safety monitor will be notified with 24 hours and she will review the medical records.
 - iv) The Safety Monitor, together with the PI, will notify the OHSU IRB, the NIH, and the CRC of serious unexpected adverse events.
- b) Annual Review. The principal investigator and MD co-investigator will review this protocol on a continuing basis for subject safety and include results of the review in the annual progress reports submitted to the IRB and NIH.
- c) Annual Report. The annual report will include a list of adverse events and the content listed below as well as a memo of findings and recommendations provided by the Safety Monitor.
- d) Content of the Annual Report. The annual report will address: a) Whether adverse event rates are consistent with pre-study assumptions; b) Reason for dropouts from the study; c) Whether all participants met entry criteria; d) Whether continuation of the study is justified on the basis that additional data are needed to accomplish the stated aims on the study; and e) Conditions whereby the study might be terminated prematurely.

VII. References Cited

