Long-chain FAO (LCFAO)-deficient subjects exhibited higher % fat mass and extramyocellular lipid content (EMCL) in soleus muscle. Percent fat mass was greater and % fat-free mass lower in LCFAO subjects than controls (**Figure 2A**).⁽³⁰⁾ Intrahepatic lipid (IHL) and IMCL content were not different between FAO patients and controls (**Figure 3A and B**).⁽³⁰⁾ However, subjects with a FAO disorder did have greater EMCL deposition compared to controls (**Figure 3A and B**), which we suspect parallels their higher % body fat (**Figure 2**), which, in turn, likely reflects their reduced capacity to oxidize fat and their more sedentary lifestyle.

Responses to oral glucose loads were identical in LCFAO-deficient subjects and matched controls. During a standard OGTT, neither fasting nor post-glucose load concentrations of glucose or insulin were different between FAO-deficient subjects and controls (**Figure 2B and C**). Estimates of insulin sensitivity were also similar between groups (**Table 1**). While our finding that, despite markedly lower FAO and greater body fat compared to controls, patients with CPT-2, VLCAD and TFP deficiency have normal glucose tolerance (and estimated insulin sensitivity and secretion) is supportive of the theory that reducing FAO cycle flux is protective against insulin resistance, these patients did not include subjects with MCAD deficiency, were not truly “metabolically stressed” by virtue of being on a low-fat diet (which could explain similar IMCL levels to controls), and did not undergo a direct measure of insulin sensitivity. Therefore, this aim will address these limitations in our pilot data by performing hyperinsulinemic-euglycemic clamps (HECs) and co-infusions of intralipids (or a control solution) and by including subjects with MCAD defects.

[figure not shown]
VLCAD-deficient mice are protected from insulin resistance on a high-fat diet. VLCAD-/- mice with a targeted deletion of exons 7-19 have a phenotype similar to humans with long-chain FAO disorders and have previously been reported to be protected from high-fat-diet-induced insulin resistance.^(21, 107) We, too, have shown this when we measured insulin sensitivity by HEC in male VLCAD-/- mice (n=6) compared

Table 1: Glucose, insulin and estimates of insulin sensitivity in CPT2 and LCHAD-deficient subjects (n=12) compared to controls (n=12).

	Subjects	Controls
Fasting glucose (mg/dl)	97 ± 14	105 ± 19
Fasting insulin (μU/ml)	17± 8	13± 5

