The following day, the clamp study will begin at approximately 6:00 AM and end at about 4:00 PM (Day 2; **Figure 11**). Indirect calorimetry to measure energy expenditure and respiratory quotient for estimation of fat oxidation will be performed in the last hour of the clamp. The order of the intralipid vs. glycerol/saline infusion during HEC will be randomly assigned. Subjects will rest overnight and consume a standardized breakfast the following day (Day 3) and be discharged to home. Subjects will return 4 months later and repeat the admission with the alternative clamp procedure. If accurate clamp results are not achieved at Visit 1 or 2, the subject may be asked to return for another study visit to repeat the clamp procedure, DEXA, indirect calorimetry and/or biopsies. During periods of hospital recommendations for decreased in-person contact, study visits will be postponed until study staff are notified of return to normal research visit operations.

¹H and ¹³C MRS Procedure: of the liver and muscle: will be performed as previously described(18, 30) prior to (-100 min) and following both clamp procedures. Each subject will complete 4 MRS measurements of liver and muscle lipid content (**Figure 11**). Image-guided, ¹H localized, MRS following high-resolution T-weighted spin-echo imaging will be performed on a Siemens 3T whole-body system. Radiofrequency surface coils will be used for region-of-interest (ROI) voxel localization and spectroscopy data acquisition. Depending on the schedule for the MRS instruments and to allow for more time for a meal before the testing, the MRS measurements may not be completed until approximately 5:30 PM.

MRI of the abdomen to quantify visceral and subcutaneous fat: Although not a primary outcome, these measures will be acquired using a Siemens 3T system as previously described (18, 30).

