HEC with co-infusion of [6,6-²H₂] glucose and intralipids will be used to determine whole-body [S_i], liver [S_{i-H}], and skeletal muscle [S_{i-M}] insulin sensitivity. Following a 10-hour overnight fast, at approximately 0600 hr, the intravenous catheters placed the evening before in one arm for infusions and in the contralateral hand for blood withdrawal will be warmed to 70°C using a warming mitt for sampling of arterialized venous blood. A primed (200 mg/m²) IV bolus followed by 2.0 mg/m² body surface area per minute constant infusion of [6,6-²H₂] glucose (Cambridge Isotope Laboratories, Andover, MA) will be infused to achieve ~1.0 mol percent excess for all subjects. Plasma samples will be obtained at -125, -120, -20, -15, -10, and -5 minutes to estimate basal endogenous glucose production and/or fasting insulin concentration. At the completion of the 2-hr infusion with glucose isotope, a primed, constant infusion of regular insulin at 40 mU/m²/min will be started and continued for 5 hours. Concurrent with the insulin infusion, either a

Figure 11: Study Protocol for Aims 1 and 2.

Participants will start a dideuterated glucose infusion 2 hours prior to the clamp. Lipid deposition will be measured by ¹H spectroscopy. The insulin infusion with either co-infusion of glycerol/saline or intralipid will begin at time 0 and last for 5 hours. Glucose will be infused at a variable rate to maintain euglycemia. At the end of the clamp, a muscle and adipose biopsy will be collected and lipid deposition re-measured.

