saline/2.5% glycerol or 20% intralipid infusion of 1.5 ml/min will be started and continued until the 5-hour clamp has been completed and the muscle and fat biopsy have been performed. Blood glucose will be monitored every 5-10 min during the insulin infusion using a Hemocue Glucose 201(HemoCue America, Brea, CA), or an i-STAT analyzer (Abbott Point of Care Inc, Abbott Park, IL) and euglycemia will be maintained throughout the clamp by infusing 20% dextrose at a variable rate. To maintain a constant enrichment of [6,6-²H₂] glucose in blood during the clamp, [6,6-²H₂] glucose infusion will be continued throughout the clamp and at 2% enrichment in the 20% dextrose solution. Additional blood samples will be collected every 60 minutes for insulin, ketones, and FFA, and at the beginning and end of the clamp for ²H₂-glucose and metabolomics. Using the blood samples collected during the 30-minute period just preceding and at the end of the glucose clamp, glucose disposal rates (Rd) and basal endogenous glucose production (R_a) will be calculated according to the steady-state equations of Steele.(92) At the end of the 5 hour infusion and completion of the muscle and fat biopsies, the insulin and intralipid or glycerol/saline infusions will be stopped. After 10 minutes, the subject will be fed a low-fat meal. Blood glucose will continue to be monitored for an additional hour after the insulin infusion is stopped with adjustment to the glucose infusion as indicated to ensure subjects reestablish endogenous glucose regulation.

Rationale for HEC approach: Patients will undergo insulin sensitivity measurement using HECs along with determination of ectopic fat accumulation by ¹H magnetic resonance spectroscopy (MRS). If the defective mitochondrial function and "lipotoxicity" hypothesis is true, then insulin resistance should be common among patients with long-chain FAO disorders in whom FAO capacity is greatly reduced. However, insulin resistance and diabetes have not been previously reported in case reports of patients with CPT2, VLCAD, or LCHAD/TFP deficiency(35) and, in our preliminary data(30) (see also above), these patients have comparable levels of IMCL, IHL, and glucose tolerance to controls while consuming a low-fat diet.

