The primary analyses to compare disease groups with healthy controls will use mixed models with a random effect for matched pair to allow for correlation between the observations on the matched observations. In addition to the random pair effect, a disease effect (disease versus healthy), and a diagnostic group effect (CPT2, VLCAD, LCHAD/TFP, MCAD), we will also incorporate a fixed effect for the order of testing (interlipid infusion tested first or second). The hypotheses focus on the comparisons between diseased individuals and their matched controls with regard to the difference in outcomes under the two conditions (glycerol vs interlipid infusion). For these analyses, we will use the difference in a given outcome (e.g., Rd uptake) between infusion conditions as the dependent variable and compare these differences between diseased and matched controls, separately for the four diagnostic groups (CPT2, VLCAD, LCHAD/TFP, MCAD). Although we will conduct a formal test of interaction of disease (disease vs healthy) and diagnostic group, we are not powered for such a test and, hence, will focus on separate inferences for the four disease groups. Note that, as indicated in the hypotheses, we expect to find differences between the controls and the CPT2, VLCAD, and LCHAD/TFP subjects, but not between the controls and the MCAD subjects. For the latter comparison, our emphasis will be on estimating the magnitude of the mean differences via 95% confidence intervals rather than formal hypothesis testing. We will use a significance level of 0.05 for each outcome comparison, with no adjustment for multiple comparisons due to the limited sample sizes. We are unable to increase sample sizes due to the small study populations and budgetary constraints, so cannot power the study to take into account the multiple comparisons. However, we will present for each outcome, both unadjusted p-values as well as p-values adjusted for the two multiple comparisons (one for each disease group) using the Holm procedure.(38)

Power Considerations:

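### Does leaving the body-size scale for Rd unstated undermine the patient–control comparison of the lipid effect?

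*Combined protocol and SAP*

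**What the plan says.** Section III (Study Design, clamp procedure) says that "glucose disposal rates (Rd) and basal endogenous glucose production (R_a) will be calculated according to the steady-state equations", with no unit or divisor. Section V (Statistical Analysis) says "we will use the difference in a given outcome (e.g., Rd uptake) between infusion conditions as the dependent variable". The model terms it names are matched pair, disease, diagnostic group and infusion order. Body composition is not among them.

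A per-kg unit appears only in Table 5, for the glucose infusion rate (GIR), in published healthy-volunteer values used for power. Power Considerations does call GIR a primary clamp result, so the unit is less open for GIR than for Rd.

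The infusions do not point to one scale. Tracer and insulin are given per m², whereas for the study infusion a "saline/2.5% glycerol or 20% intralipid infusion of 1.5 ml/min will be started", which is a flat rate.

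In E.1 (Preliminary Data), 12 long-chain patients (2 CPT-2 and 10 TFP/LCHAD) were compared with 12 controls matched on age, sex and BMI, and "Percent fat mass was greater and % fat-free mass lower in LCFAO subjects than controls". The size of that gap is in a figure that is not shown. Section II again matches on age, sex and BMI (within 2 kg/m²) and requires low-activity controls. DEXA lean mass is measured at each admission.

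Basal Ra is a separate matter. "Plasma samples will be obtained at -125, -120, -20, -15, -10, and -5 minutes to estimate basal endogenous glucose production", whereas "The insulin infusion with either co-infusion of glycerol/saline or intralipid will begin at time 0 and last for 5 hours". Basal Ra therefore precedes the lipid and cannot carry the lipid contrast.

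**The concern.** A crossover removes additive differences between people. It does not remove a multiplicative one when the outcome is an absolute difference. Dividing each person's Rd by body weight or by fat-free mass rescales both days and hence the drop between them. If patients carry less fat-free mass per kg of weight, the same data show a smaller patient drop, and so more apparent protection, per kg weight than per kg fat-free mass.

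Protection of long-chain patients is the trial's central hypothesis. Each diagnosis has 8 pairs, tested at 0.05 without a binding multiplicity adjustment. If no scale is fixed, it could be chosen after the results are seen, and an intermediate result could be read either way.

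**Working it through.** **Inputs.** From Table 5: GIR 57.2 ± 9.3 (glycerol) and 25.7 ± 7.8 (lipid); hypothesised drops 31.5 in controls and 5.7 in long-chain patients, a difference of 25.8. From section II: 8 pairs per diagnosis. GIR stands in for Rd because no Rd mean or SD is given. Assumed: a relative deficit q in patients' fat-free fraction of 5% to 15%, and a control fat-free fraction f of 0.75.

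**The plan's own figure.** With zero correlations, the SD of a within-person change is √(9.3² + 7.8²) = 12.14, and the SD of a pair difference is 12.14 × √2 = 17.17. A paired t-test with n = 10 then has 98.8% power for 25.8, against about 97% stated. The same method gives 62.6% and 78.1% for PDK4, against 63% and 78% stated. The method is close enough to use.

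**How far the scale moves the contrast, with no true protection.**
- Equal drop per kg fat-free mass: 31.5 × q = 1.6 to 4.7.
- Equal drop per kg weight: 31.5 × (1/(1 − q) − 1) = 1.7 to 5.6.
- As a share of 25.8: 6% to 22%.

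**At the hypothesised patient drop.** 5.7 × (1/(1 − q) − 1) = 0.3 to 1.0. With zero correlations and 8 pairs, power is 95.2% per kg weight and 93.7% to 89.2% per kg fat-free mass.

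**Which scale is biased.** Let a be adipose tissue's share of the drop. The spurious control-minus-patient difference per kg weight is W = 31.5 × q × (1 − a − a·f/(1 − f)), which at f = 0.75 is 31.5 × q × (1 − 4a). If instead the drop per kg fat-free mass rises as (lipid per kg fat-free mass)^e at equal body weight, W = 31.5 × (1 − (1 − q)^(1 − e)). On the fat-free-mass scale, in control-equivalent units, the difference is 31.5 − (31.5 − W)/(1 − q). Positive values favour protection.

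| Assumption | Per kg weight | Per kg fat-free mass |
|---|---|---|
| Disposal follows fat-free mass | +1.6 to +4.7 | 0 |
| Adipose share 10% | +0.9 to +2.8 | −0.7 to −2.2 |
| Adipose share 25% | 0 | −1.7 to −5.6 |
| Adipose share 30% | −0.3 to −0.9 | −2.0 to −6.7 |
| Lipid-dose effect, e = 0.5 | +0.8 to +2.5 | −0.8 to −2.7 |
| Lipid-dose effect, e = 1 | 0 | −1.7 to −5.6 |

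The documents do not select a row. E.2 credits muscle with up to 70% of glucose uptake and says that adipose tissue contributes, but gives no adipose share. No lipid dose-response is given.

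**False-positive rate.** This uses the per-kg-weight scale under strict proportionality, 8 pairs, a two-sided 5% paired t-test, and correlations from 0 to 0.50. It is 5.6% to 7.3% at q = 5% and 10.4% to 26.8% at q = 15%. With e = 0.5 the highest value is 10.8%. These rates are illustrative, since they use GIR SDs and not the planned mixed model.

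**Percentage change.** Under proportionality both groups drop 31.5/57.2 = 55.1% on either scale, so the divisor cancels if body composition is stable between visits.

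**The case for a change.** The best case for a change is that an uncertain direction is itself a reason to fix the scale in advance. The imbalance comes from the trial's own pilot, the matching repeats the pilot's variables, DEXA is already planned, and only wording would change. Fat-free mass could be defended as the cautious primary scale, because an adipose share or a lipid-dose effect works against a finding of protection on it.

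Part of this stands. Rd has no stated unit, the crossover does not cancel a divisor, and a partial drop in patients is the result most sensitive to scale. A report should name the divisor and show the alternatives.

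The case for mandating one scale is weaker. Fat-free mass shows the larger worst-case bias in the table (6.7 against 4.7), and a bias against protection can hide a real effect. Insulin per m² also gives patients more insulin per kg fat-free mass at equal surface area, and the direction of its effect on the lipid-induced drop is unknown. Percentage change has as good a claim to be primary, since Power Considerations frames the GIR hypothesis as a drop below 10%.

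The upper false-positive figure needs the largest assumed deficit, the highest correlations and strict proportionality together. E.1 links the patients' higher body fat partly to inactivity, so low-activity controls may narrow the gap below the assumed range. The pilot lists no VLCAD or MCAD patients and only two with CPT-2, so the imbalance is undocumented or thinly supported there.

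**Conclusion.** No change to the plan is needed. The unstated unit for Rd is a detail that analysts can fill sensibly: lean mass and weight will be available, and a report can give Rd per kg weight, per kg fat-free mass and as percentage change side by side. Choosing one as primary is a trade-off that the documents cannot resolve, because no scale is neutral across plausible assumptions.

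The scale shifts the contrast by about 1.6 to 5.6 µmol/kg/min with no true protection, and by 0.3 to 1.0 at the hypothesised patient drop. It cannot produce the full hypothesised difference of 25.8. These sizes rest on an assumed 5% to 15% deficit in fat-free fraction and on GIR standing in for Rd. The explant glucose-uptake and insulin-signalling measures in Aim 2 address protection without any whole-body divisor.

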A. During fatty acid excess, long-chain acyl-CoAs and IMCL will accumulate, but decreased FAO will prevent an increase of redox equivalents and ROS generation resulting in normal insulin signaling and glucose uptake. **B.** With increased FAO upstream from MCAD, IMCL will still accumulate, but excess redox equivalents will lead to an oxidized mitochondrial environment with ROS generation, activation of serine kinases, inhibition of insulin signaling and decreased glucose uptake. IMCL=intramyocellular lipid. LCFAO = long-chain fatty acid oxidation. MCFAO = medium chain fatty acid oxidation. TCA = tricarboxylic acid cycle. ETC = electron transport chain. ROS= reactive oxygen species. PKC = protein kinase C.

[figure not shown]
infusion will increase IMCL in FAO patients and controls alike (**Figure 5A and B**). After the intralipid infusion, respiratory quotients will reflect FAO capacity and will be highest (indicating greater carbohydrate oxidation) in subjects with CPT2, VLCAD or LCHAD/TFP deficiency and lower (indicating greater fat oxidation) in MCAD-deficient subjects and controls. Based on our preliminary data of normal OGTTs in patients with inherited defects in the FAO defects, our findings of protection from high-fat-diet-induced insulin resistance in VLCAD $-\text{}/-$ mice, as well as studies that have shown that blocking FFA entry into mitochondria can alleviate high-fat-diet-induced insulin resistance in animal models,(56, 57) we anticipate that subjects with defects in CPT2, VLCAD, and LCHAD/TFP enzymes will be protected from high-fat-diet-induced insulin resistance, essentially "blocking" long-chain FA oxidation (flux) at a level that avoids accumulation of metabolic intermediates that adversely affect insulin signaling (**Figure 5A**). On the other hand, we anticipate that increased oxidative flux of fatty acids from long-chain fatty acids to medium chain metabolites will not provide the same protection from excess fatty acid substrate, impairing insulin signaling in patients with MCAD deficiency (**Figure 5B**) who will exhibit insulin resistance (compared to control infusion days) in muscle (reduced glucose disappearance, reduced insulin signaling ex-vivo), and adipose tissue (reduced suppression of FFA during the clamp) similar to controls. We predict that the degree of FFA-induced insulin resistance in these subjects will be similar to control subjects (**Figure 5B**).

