Glucose and FFA are the two major substrates used for the synthesis of triglycerides in WAT. We have developed a fluorescent-based approach for simultaneous measurement of glucose and FFA uptake using green fluorescent 2-NBD-glucose and red fluorescent BODIPY-C12(97) (**Figure 7**). This approach will allow determination of insulin sensitivity and lipid and glucose accumulation of primary WAT explants. In addition, small soleus muscle biopsies will be analyzed for insulin sensitivity using 2-NBD-glucose (**Figure 8**).

Anticipated results:

Mirroring increases in ectopic fat we expect to see in Aim 1, we anticipate that intralipid infusion, but not infusion of the control solution, will increase plasma FFA's associated with increased muscle and adipose triglycerides and DAG's in all FAO patients and controls (**Figure 5**). Plasma and tissue long-chain acylcarnitines will be greatly elevated in CPT2, VLCAD or LCHAD/TFP-deficient subjects; medium-chain acylcarnitines will be greatly elevated among subjects with MCAD deficiency; and both long-chain and medium-chain acylcarnitines will be only modestly elevated in normal controls. Based on our preliminary data, we expect that short-chain acylcarnitines may be elevated in subjects with CPT2, VLCAD, LCHAD/TFP, and MCAD deficiency compared to controls.

We predict that these cellular changes will be associated with a decrease in phospho-(p)IR and pAKT and an increase in pPKC- Θ in subjects with MCAD deficiency and control subjects, but not in CPT2, VLCAD, and LCHAD/TFP-deficient subjects, paralleling the expected outcomes of system insulin sensitivity measurements obtained by the HEC's in Aim 1. These expected decreases in insulin signaling pathway component expression and activation will also be reflected by decreased glucose uptake into muscle and adipose tissue and decreased FFA uptake into adipose in controls and subjects with MCAD deficiency. Decreased glucose uptake will be correlated with medium-chain acylcarnitines, as has been reported in human studies(52) and in cultured myocytes.(52) We anticipate no change in glucose and FFA uptake in muscle or adipose tissue from the glycerol/saline to the intralipid co-infusion samples in CPT2, VLCAD and LCHAD/TFP-deficient subjects.

[figure not shown]
Figure 8: Fluorescence analysis of glucose uptake in monkey skeletal muscle.

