Because a low-fat diet is standard therapy for these patients, previous clinical reports and our preliminary data could be argued to lack the proper conditions to permit accumulation of insulin resistance-inducing cytosolic lipid byproducts. However, prolonged high-fat feeding is contraindicated in FAO patients due to increased risk of hypoglycemia and rhabdomyolysis (see also Human Subjects). Instead, we propose creating a "fat challenge" by infusing intralipids (20% IL, 1.5 mL/min+heparin) during a HEC, which has been shown to increase IMCL and induce insulin resistance within 4 to 6 hours.(4, 9, 11, 94) From studies using an identical intralipid infusion protocol, levels of non-esterified free fatty acids in the blood can range between 0.3 to 4.5 mmol/L (mean 1.49 mmol/L).(4, 8, 9, 11, 17, 27, 28, 36, 39, 60, 73, 81, 82, 89, 90) In comparison, non-esterified fatty acid (NEFA) levels have been reported to rise up to 0.8 - 2 mmol/L in adults and children after an overnight fast(7, 10, 83, 95) and up to 0.8 - 1.0 mmol/L after a high-fat meal.(87)

Safety: By performing a HEC during the intralipid infusion, hypoglycemia and rhabdomyolysis are avoided through the variable glucose infusion to maintain glucose levels in a safe range and NEFA levels remain closer to physiological levels. Therefore, we feel the intralipid + HEC protocol proposed can be conducted safely among FAOD subjects while achieving high insulin and high NEFA levels. By using a co-infusion of dideuterated glucose, we will be able to separately measure glucose appearance in the fasting state (R_a; mostly hepatic glucose output) as well as insulin-induced glucose disposal (Rd; mostly muscle), as there is reason to predict that FAO defects may affect these two organs separately.(104, 105) Using a randomized, crossover design, the change in insulin sensitivity with co-infusion of intralipid will be compared between FAO patients and matched controls to a control infusion (glycerol / saline).

Tissue Biopsies: Blood, muscle, and adipose tissue samples will be collected near the end of each clamp to allow determination of both changes in serum and intracellular energy metabolites and tissue-specific insulin sensitivity *ex vivo*.

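### Weaker FFA suppression on the intralipid day cannot be read as adipose insulin resistance, because the infusion itself raises plasma FFA

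*Combined protocol and SAP*

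**What the plan says.** - **Specific Aim 1, Anticipated Results.** The prediction concerns MCAD patients, "who will exhibit insulin resistance (compared to control infusion days"). For fat, the readout named is "adipose tissue (reduced suppression of FFA during the clamp) similar to controls". The comparator is the same subject's glycerol/saline day.
- **Specific Aim 2, Anticipated results.** The protocol expects that "intralipid infusion, but not infusion of the control solution, will increase plasma FFA's", along with increases in "muscle and adipose triglycerides and DAG's in all FAO patients and controls".
- **III. Study Design, rationale for the clamp and the safety paragraph after it.** From studies with an identical infusion, "levels of non-esterified free fatty acids in the blood can range between 0.3 to 4.5 mmol/L (mean 1.49 mmol/L"). For comparison, NEFA levels "have been reported to rise up to 0.8 - 2 mmol/L in adults and children after an overnight fast". The stated aim is "achieving high insulin and high NEFA levels".
- **III. Study Design, clamp procedure.** "saline/2.5% glycerol or 20% intralipid infusion of 1.5 ml/min will be started and continued until the 5-hour clamp has been completed" and the biopsies are done. FFA is sampled hourly. The only tracer is dideuterated glucose.
- **IV. Study Procedures, Lab Assays.** FFA is measured by an enzymatic colorimetric kit, that is, as a total concentration.
- **V. Statistical Analysis.** For any given outcome, the between-infusion difference is the dependent variable and is compared between patients and matched controls, separately by diagnosis.

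**The concern.** A fall in plasma FFA under insulin reflects adipose insulin action when the FFA comes from the subject's own fat stores. On the intralipid day, fatty acid is also supplied from outside for the whole clamp, and raising plasma FFA is the purpose of the infusion. The measured quantity is then partly the exposure itself.

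The plan has no means of splitting the two sources. A glucose tracer says nothing about fatty acid turnover. Plasma glycerol is not a clean substitute marker of lipolysis, because the control solution contains 2.5% glycerol.

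Two misreadings follow. Controls and MCAD patients would look adipose-resistant, as predicted, whether or not their adipose tissue changed. Long-chain patients, who are predicted to be protected but are also expected to have raised FFA, could be labelled resistant on the same readout. At stake is what the trial may say about adipose tissue from plasma FFA.

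**Working it through.** The plan gives no figure for FFA suppression, so there is none to reproduce. The check asks what the readout does when adipose insulin action is held the same on both days.

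**Set-up.** Let F0 be fasting FFA, s the true fractional suppression of adipose FFA release by insulin (same on both days), and E the part of plasma FFA that comes from the infused lipid. Apparent suppression is S = 1 − (clamp FFA)/F0, with clamp FFA = E + F0(1 − s).

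- Control day (E = 0): S = s.
- Intralipid day: S = s − E/F0.
- Apparent loss of suppression with nothing changed in fat: **E/F0**, which is positive whenever E is positive.

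**With the protocol's cited levels.** If clamp NEFA is 1.49 mmol/L, then S = 1 − 1.49/0.8 = −86% for a fasting value of 0.8, and 1 − 1.49/2.0 = +25.5% for 2.0. If all of the 1.49 were infused lipid, these would be the readings with adipose release completely shut off (s = 100%).

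**Illustration under assumed values.** The documents do not give E, s or mean fasting FFA for these groups. I assume E from 0.3 to 1.49 mmol/L, F0 from 0.5 to 2.0 mmol/L, and s from 50% to 100%.

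| F0 | E | s | Control-day S | Intralipid-day S | Apparent loss E/F0 |
|---|---|---|---|---|---|
| 2.0 | 0.3 | 80% | 80% | 65% | 15 points |
| 0.8 | 0.75 | 80% | 80% | −14% | 94 points |
| 0.8 | 1.49 | 100% | 100% | −86% | 186 points |
| 0.5 | 1.49 | 50% | 50% | −248% | 298 points |

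The width, 15 to 298 points, reflects the assumptions. The sign does not depend on them.

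**Does the planned contrast cancel it?** With true suppression unchanged in both groups, the patient-minus-control contrast of the between-day difference still contains E_p/F0_p − E_c/F0_c. On the percentage scale it cancels only if those ratios are equal; on the mmol/L scale, only if E_p = E_c. Three features of the plan make equality doubtful:

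- Long-chain patients oxidise long-chain fatty acid less, by selection, so E_p may be higher.
- Their fasting FFA was higher than controls' in the sponsor's pilot data (Aim 2, Preliminary Data), so F0_p differs.
- The infusion rate is fixed in ml/min. Matching on sex and BMI limits, but does not remove, differences in body size and composition.

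The first two features pull in opposite directions on the percentage scale. For example, take E = 0.75 in both groups, F0 = 0.8 in controls and 1.0 in patients (assumed). The losses are 0.75/0.8 = 94 points and 0.75/1.0 = 75 points, a spurious advantage of 19 points for patients. It vanishes only if E_p is 0.75 × 1.0/0.8 = 0.94, and reverses above that. The residual bias in the contrast therefore has no predictable sign.

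**The case against.** The strongest reply is that this is no specified endpoint. The wording is a parenthesis in a section of predictions. The clamp procedure sets out whole-body, liver and muscle insulin sensitivity, with no adipose index. Only Rd and Ra are calculated, the Aim 1 hypotheses concern ectopic fat, Rd and Ra, and power rests on GIR and PDK4. Adipose insulin action belongs to Aim 2, where explant glucose and FFA uptake and insulin receptor and Akt phosphorylation are compared between infusions. The patient-minus-control contrast also removes any infusion effect common to both groups.

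Most of this stands and sets the scope of the point. It does not rescue the readout. The parenthesis is an explicit interpretive rule, the analysis section applies the between-infusion difference to any outcome without excluding FFA, and the within-group reading against control days gets no protection from the contrast. The pilot finding that patients' FFA fell normally came from an oral glucose load without infused lipid.

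A reader might infer more than the documents support:

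- *That the artefact falsely confirms the trial's hypothesis.* The hypothesis is a contrast between groups. An artefact present in all of them would produce the predicted result in controls and MCAD patients but contradict the long-chain prediction. For MCAD versus control, the plan emphasises confidence intervals over formal testing.
- *That every subject will appear resistant.* The cited NEFA range reaches down to 0.3 mmol/L, so an individual could still show a net fall. The argument concerns group means.
- *That the adipose question cannot be answered.* The Aim 2 assays do not use plasma FFA.
- *That −86% to +25.5% estimates the effect.* It sets fasting values described as upper levels, in adults and children, against a mean from other studies. No control-day clamp FFA is given.

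**Conclusion.** The concern holds in a limited form, and its severity is moderate. Within any group, mean FFA suppression will look reduced on intralipid even with unchanged adipose insulin action, so the predicted finding in controls and MCAD patients is not evidence of adipose resistance, and long-chain patients could be misread as resistant. The patient-minus-control contrast would remove this only under equal FFA effects of the infusion, which the design gives reason to doubt.

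Only the direction of the within-group bias is established; the size is not estimable from the documents. The conclusion assumes that infused lipid contributes some plasma FFA, as the protocol itself expects, and that fasting FFA is on average the same at the two visits, which the randomised order supports. Rd, GIR and the Aim 2 adipose assays are unaffected, so no powered outcome is in question.

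**What to change.** Amend the Aim 1 Anticipated Results and add a matching line to V. Statistical Analysis:

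1. Drop the between-infusion difference in FFA suppression as evidence of adipose insulin resistance.
2. Use FFA suppression as an adipose measure only on the glycerol/saline day, patient versus matched control. Name the pre-insulin and late-clamp samples that define it, and report it in mmol/L and as a percentage, since fasting FFA may differ between groups.
3. Base the intralipid effect on adipose tissue on the Aim 2 biopsy measures already planned: insulin receptor and Akt phosphorylation, and explant glucose and FFA uptake.
4. Report intralipid-day FFA by group as a check on the lipid exposure achieved.

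Heparin appears with the lipid in the clamp rationale and in the list of expected risks, but not in the infusion procedure. These passages should be reconciled, because they bear on how intralipid-day FFA is interpreted.

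The cost is protocol and SAP wording. FFA is already sampled hourly at both visits and the biopsies are already taken, so no new visits or tissue are needed.
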